C.5 Image preprocessing: Raw BOLD data will be pre-processed using SPM8 (website: http://www.fil.ion.ucl.ac.uk). After discarding the first four volumes for saturation effects, motion correction will be applied with a 3D rigid body transformation. Subjects with head movement >2mm will be excluded. fMRI images will be spatially normalized to Montreal Neurological Institute (MNI) space by registering each subject's fMRI images to their high resolution T1W scan, which will be registered to MNI space using the DARTEL method. Registered fMRI images will be spatially smoothed using a 4mm FWHM isotropic Gaussian kernel. Band-pass filtering (0.01Hz–0.08Hz) will be applied to reduce effects of low frequency drift and high-frequency physiologic noise. fMRI data will be corrected for movement parameters (3 rotational and 3 translational variables) as well as global, CSF, and white matter signal fluctuations.

C.6 Seed Based Insular Functional Connectivity: Using customized MATLAB scripts, whole brain voxel-wise connectivity maps will be calculated according to Margulies et al. from the 10 minute RS-fMRI exams using a seed-based approach with a 5mm radius sphere centered at the right anterior insular rTMS target. To compare insular connectivity, first we will apply a fixed-effects analysis to each subject's resultant whole-brain insular connectivity maps to investigate individual brain connectivity differences associated with treatment. Treatment and group comparisons will be performed using ANCOVA. These comparisons will provide results for **Aim #2**.

C.7 Craving cue task-based insular activity: After resting state fMRI examinations, all subjects will perform smoking cue/neutral cue craving tasks during a 15 minute fMRI using the aforementioned imaging parameters. We have previous experience using this task to elicit food craving. We will use an identical visual cue paradigm, but will replace the food-cue images with the international smoking image series. Each run will consist of pseudorandom presentations of different smoking-related and food-related images. Between images, participants will be asked to fixate on a cross image for variable duration of time to introduce jitter into the design and improve fit of the generalized linear model (GLM).

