# F.2 Aim 2: Determine if insular TMS alters insular connectivity:

F.2.1 Statistical Design: A second-level random effects model will be used to compare insular connectivity by treatment and group using ANCOVA. Age will be controlled for as nuisance variables. A Monte Carlo cluster correction threshold will be applied to correct for multiple comparisons, using a voxel-wise p<0.005 and family-wise p < 0.05.

F.2.2 Sample Size and Power Analysis: Hanlon et al. measured fMRI connectivity changes after rTMS to two separate prefrontal targets, resulting in Cohen's *d* values greater than 1.9. Based on these estimates, our target recruitment goal must be greater than 6 in each arm (total n=12) to detect significant differences with 80% power and 0.05 significance level. Our sample size n=32 (after 10% attrition of fMRI data, 10% attrition of TMS administration) is similar or larger compared to other studies using similar methods. With a sample size of 32, we can detect a correlational effect size as small as 0.30 ( $f^2$ ) with 80% power and 0.05 significance level.

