# F.3 Aim 3: Determine if insular TMS alters insular activity:

F.3.1 Statistical Design: Contrast maps of smoking>neutral cues will be analyzed using secondlevel random-effects to compare these contrasts within and between treatment groups using ANCOVA. Two separate task-based analyses will be performed: (1) insular ROI analyses by extracting insular activity from the fMRI with a 5mm radius sphere centered at the insular TMS target, and (2) whole brain analysis. Both analyses will control for multiple comparisons and nuisance variables as we will in Aim #2.

F.3.2 Sample Size and Power Analysis: Hanlon et al. measured fMRI activity changes after rTMS to two separate prefrontal targets, resulting in Cohen's *d* values greater than 2.3. Based on these estimates, our target recruitment goal must be greater than 5 in each arm (total n=10) to detect significant differences with 80% power and 0.05 significance level. Our sample size n=32 (after 10% attrition of fMRI data, 10% attrition of TMS administration) is similar or larger compared to other studies using similar methods. With a sample size of 32, we can detect a correlational effect size as small as 0.30 ( $f^2$ ) with 80% power and 0.05 significance level.

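### The 80% power in F.2.2 and F.3.2 is that of one uncorrected test at 0.05, so it is unsupported for the planned whole-brain, cluster-corrected analyses

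*Combined protocol and SAP*

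**What the plan says.** F.2.1 sets the decision rule for Aim 2: "A Monte Carlo cluster correction threshold will be applied to correct for multiple comparisons, using a voxel-wise p<0.005 and family-wise p < 0.05". C.6 fixes the search space, since from the insular seed "whole brain voxel-wise connectivity maps will be calculated". F.3.1 gives Aim 3 two analyses, a 5 mm insular sphere and a whole-brain map, and applies the Aim 2 multiplicity control to both.

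The power paragraphs mention neither the voxel threshold nor the cluster rule.

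- F.2.2 takes Cohen's d "values greater than 1.9" from a cited TMS-fMRI study and concludes that recruitment "must be greater than 6 in each arm (total n=12) to detect significant differences with 80% power and 0.05 significance level".
- F.3.2 takes d above 2.3 from the same study and says the target "must be greater than 5 in each arm (total n=10"), again at 80% power and 0.05.
- Both paragraphs add that with the 32 participants left after attrition "we can detect a correlational effect size as small as 0.30" (f²), at the same power and level.

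**The concern.** The error level in the power calculation is not the one in the analysis. F.2.1 and F.2.2 are adjacent, yet the first declares an effect only through a voxel threshold ten times stricter than 0.05 followed by a cluster rule, and the second computes power as though one comparison were made at 0.05. This is separate from whether d=1.9 or d=2.3 are suitable effects: the mismatch would remain with any other values.

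At stake is what a reader may take from the imaging results. If no cluster survives, the quoted detectable effects suggest that the whole-brain tests could have found effects for which their power has not been shown.

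**Working it through.** **Inputs.** From F.2.2: d=1.9, 6 per arm, 80% power, 0.05. From F.3.2: d=2.3, 5 per arm, same power and level. From F.2.1: voxel-wise 0.005. Analysable sample: 40 × 0.9 × 0.9 = 32.4, so 32, or 16 per arm. Sidedness is not stated; two-sided is assumed and one-sided is shown as a variant.

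**Formula.** For two arms of n, power = P(T > t(1−α/2; 2n−2)), where T is noncentral t with 2n−2 df and noncentrality δ = d√(n/2). The opposite tail is negligible.

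**Reproducing the plan's minima at 0.05.**
- d=1.9, n=6: δ = 1.9 × √3 = 3.29, critical t 2.228, power 84.2%. Five per arm gives 74.9%, so 6 is the minimum.
- d=2.3, n=5: δ = 2.3 × √2.5 = 3.64, critical t 2.306, power 88.8%.

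A one-sided t-test would give minima of 5 and 4, and a normal approximation 5 and 3. The plan's figures are those of one uncorrected two-sided t-test at 0.05.

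**Same calculation for a single voxel at two-sided 0.005.**

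| d | n per arm | Power at 0.05 | Power at 0.005 |
|---|---|---|---|
| 1.9 | 6 | 84% | 44% |
| 1.9 | 7 | 90% | 57% |
| 2.3 | 5 | 89% | 48% |
| 2.3 | 6 | 95% | 65% |
| 1.9 | 16 | 99.9% | 98.6% |

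The rows for 7 and 6 per arm allow for the plan's wording, which says greater than 6 and greater than 5 but totals 12 and 10. At one-sided 0.005, 6 per arm (d=1.9) has 57% and 5 per arm (d=2.3) has 62%. Solving for the smallest d with 80% power at 16 per arm gives 1.02 at 0.05 and 1.38 at 0.005.

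**The f² figure at N=32.** By Fisher z, the smallest r is tanh((1.960 + 0.842)/√29) = 0.478, and f² = r²/(1−r²) = 0.296, which is the plan's 0.30. At 0.005, r = tanh((2.807 + 0.842)/√29) = 0.590 and f² = 0.53. A one-predictor F test gives 0.26 at 0.05 and 0.48 at 0.005. If f²=0.30 were tested at 0.005, power would be 50% (Fisher z) to 54% (F test).

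**From voxel to cluster.** The planned test declares a cluster, so single-voxel power is only a proxy. A small simulation shows how loose it is, with d=1.9, 6 per arm, two-sided 0.005, a uniform effect in a sphere, Gaussian noise and 150 runs per setting. It used the plan's 3.4 mm voxels and the extent above 23 voxels from the preliminary study, which is not stated for F.2.1. Per-voxel power stayed near 44%. The chance of a surviving cluster was 2% for a 33-voxel effect with 4 mm noise smoothness and 20% with 8 mm, but 88% or more for a 123-voxel effect. Smoother data would in practice need a larger extent threshold, so these values are illustrative only.

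**The case against.** The strongest reply is that 0.005 only forms clusters, while the declared error rate is family-wise 0.05. An extended effect gives many voxels a chance to join a surviving cluster, so power at one voxel is not the power of the planned test. This stands. A reader might infer that true power is 44%, or lower still because the cluster rule comes on top. The documents do not support that: they give neither effect extent nor smoothness for this test, and power could lie on either side of the proxy. Nor do they support any particular replacement minimum per arm.

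Three further limits also stand.

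- A reader might infer that the trial is underpowered for its own assumed effects. It is not on this measure: 16 per arm keeps 98.6% voxel-level power at d=1.9.
- The f² figure is called correlational. The matching analysis is the brain-behaviour regression in C.9, which states no threshold, so the 50% to 54% holds only if that regression is run voxel-wise at 0.005.
- The Aim 3 sphere, averaged to one value, is close to a single test, and 0.05 could suit it.

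Section G states how a null would be interpreted without citing any detectable effect, so correcting these figures would not by itself alter that text.

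The reply does not rescue 0.05 as the family-wise level. The minima come from a one-test formula with no search volume, cluster size or smoothness in it.

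**Conclusion.** The mismatch is real and its effect is limited. F.2.2 and the whole-brain part of F.3.2 quote 80% power for a test that the plan will not run on the whole-brain maps, so that power is unsupported there. On the single-voxel proxy, the quoted minima fall from 84% to 44% and from 89% to 48%, and the detectable between-arm d at 16 per arm rises from 1.02 to 1.38. These figures assume two-sided testing, the plan's own d values, a simple two-group comparison without the age covariate, and 32 analysable participants. They describe one voxel and do not bound cluster-level power. The sample size stands; the statements about what it can detect need correcting.

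**What to change.** 1. In F.2.2 and F.3.2, limit the 0.05 figures to a single pre-specified ROI test, for example the averaged 5 mm insular sphere in Aim 3, and say that this test is run at 0.05. Aim 2 names no such test at present, so its 0.05 figures need one specified or should be dropped.
2. For the whole-brain tests, restate the detectable between-arm effect at n=32 under the planned voxel and cluster rule. Simulation with stated smoothness, effect extent and cluster size is best. Otherwise give a voxel-level d of about 1.4, labelled as a proxy that may lie above or below cluster-level power.
3. State which analysis f²=0.30 describes. If it is a voxel-wise regression at 0.005, replace it with about 0.48 to 0.53, depending on the method used.

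The cost is rewriting two paragraphs, plus a modest simulation if that route is taken. The stated detectable effect becomes less favourable. No extra participants and no change to the analysis are needed.

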# F.3 Aim 3: Determine if insular TMS alters insular activity:

F.3.1 Statistical Design: Contrast maps of smoking>neutral cues will be analyzed using secondlevel random-effects to compare these contrasts within and between treatment groups using ANCOVA. Two separate task-based analyses will be performed: (1) insular ROI analyses by extracting insular activity from the fMRI with a 5mm radius sphere centered at the insular TMS target, and (2) whole brain analysis. Both analyses will control for multiple comparisons and nuisance variables as we will in Aim #2.

F.3.2 Sample Size and Power Analysis: Hanlon et al. measured fMRI activity changes after rTMS to two separate prefrontal targets, resulting in Cohen's *d* values greater than 2.3. Based on these estimates, our target recruitment goal must be greater than 5 in each arm (total n=10) to detect significant differences with 80% power and 0.05 significance level. Our sample size n=32 (after 10% attrition of fMRI data, 10% attrition of TMS administration) is similar or larger compared to other studies using similar methods. With a sample size of 32, we can detect a correlational effect size as small as 0.30 ( $f^2$ ) with 80% power and 0.05 significance level.

# G. Summarize Knowledge to be Gained:

Regardless of the results of our aims, this proposal will lead to significant future research directions. In the unexpected case that no differences in craving or fMRI are observed after insular rTMS, our interpretation will be that the insula is not as critical a neural node as the literature to date reports. This null result would direct our future efforts toward prefrontal targets, which has been previously demonstrated to be effective in craving mitigation. If we find that the insula is indeed an important neural node in craving behavior, these preliminary studies would pave the way for future, more sophisticated studies that compare and combine insular rTMS with prefrontal rTMS, characterize the laterality of the insula, and investigate the durability of craving mitigation with repeated rTMS as a potential long-term adjuvant treatment for nicotine dependence. Literature to date strongly support the latter conclusion, and we expect to find significant results. Regardless of outcome, this proposal will answer a critically important question for the millions of patients unable to stop smoking: how important is the insula in cigarette craving, and can insular rTMS reduce cigarette craving?

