Lastly, subjects will complete the Barratt Impulsiveness Scale, version 11 (BIS-11). This is a 30-item self-reported questionnaire used to measure impulsivity; subjects rated whether phrases and words describing aspects of impulsivity are self-descriptive.

*C.2 MRI scan acquisition parameters:* Prior to the MRI scan, subjects will be asked to complete the standard *UC Denver Brain Imaging Center MRI Research Subject Screening Form* to ensure they are safe to be scanned. Before and after rTMS, RS-fMRI and task-based fMRI examinations will be performed. This is a required component of any MRI examination. All scans will be performed on a research-dedicated 3.0 T Seimens Skyra MR system using a 20-channel head-neck coil. A VacFix head-confirming vacuum cushion will mitigate effects of head motion. High-resolution 3D T1-weighted scans will be acquired before treatment for image registration and normalization. Linear and second order shimming will be performed to reduce static field inhomogeneities at the skull base prior to fMRI scans. T2\* weighted echo-planar imaging blood oxygen level dependent fMRI will be acquired before and after treatment: (1) a 10 minute RS-fMRI, in which subjects will be asked to lay quietly in the scanner and not think of anything in particular; and, (2) a 15 minute task-based fMRI exam during a cigarette craving cue task.

C.3 1H-Magnetic Resonance Spectroscopy (MRS): Before and after rTMS, 1H-MRS examinations will be performed to quantify GABA, Glutamate, and Glutamine levels in the insula. 1H-MRS sequences will be used, as previously reported and used by colleagues in the Department of Radiology. This MR sequence will be used for exploratory analysis.

C.3 rTMS Treatment: Subjects in the insular rTMS treatment arm will undergo a single 25 minute train of 1Hz rTMS targeting the right insula16,17,54 anterior (MNI coordinates: [32, 18, 4]) at 90% motor threshold using the commercially available MagStim coil Brainsight Rapid2 and frameless stereotactic TMS localization system. Subjects in the sham rTMS treatment arm will have a sham coil placed in the same position. The sham coil

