Task-based fMRI exams will be preprocessed as above. Data will be modeled in SPM8 using a GLM with customized square waveforms representing the condition (i.e., cigarette versus neutral stimulus) and duration of stimulus convolved with a canonical hemodynamic response function.

Contrast maps of smoking>neutral cues will be analyzed using second-level random-effects to compare these contrasts within and between treatment groups using ANCOVA. Two separate task-based analyses will be performed: (1) insular ROI analyses by extracting insular activity from the fMRI with a 5mm radius sphere centered at the insular TMS target, and (2) whole brain analysis. Both analyses will control for multiple comparisons using cluster-based correction for family-wise error p<0.05. These comparisons will provide results for **Aim #3**.

C.8 Resting state network analysis (secondary): One inherent limitation of the seed-based connectivity approach is that the resultant connectivity maps are highly dependent upon ROI selection. To circumvent the potential interference caused by seed selection, secondary investigation of the functional connectome will be performed using group independent component analysis to make inferences using the GIFT toolbox (http://icatb.sourceforge.net) and using the same method and analysis pipeline as our preliminary data. Resultant resting state network connectivity maps will be compared by group to investigate differences in strength and direction of connectivity between salience, default mode, and executive control networks.

C.9 Brain-behavior relationships (secondary): Secondary analysis of brain-behavior relationships will be conducted using a GLM in SPM8 by regressing insular connectivity and activity (see C.3.6) against craving and dependence measures. This will characterize the relationship between behavior (**Aim #1**) and brain function (insular connectivity [**Aim #2**] and activity [**Aim #3**]).

C.10 Relative concentrations of GABA, glutamate, and glutamine after rTMS (exploratory): Exploratory analysis of the changes in GABA, glutamate, and glutamine concentrations induced by rTMS will be performed using spectroscopic peak detection methods and ANCOVA.

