# F. Data Analysis Plan:

# F.1 Aim 1: Determine if insular TMS reduces cigarette craving:

F.1.1 Statistical Design: For a multivariate analysis of covariance model, we will fit a general linear multivariate model, with measures of craving before and after treatment as the outcomes. As predictors, we will fit indicator variables for treatment assignment, and FTND. We will use the Hotelling-Lawley test to assess treatment by time interaction, and the main effects of time and treatment.

F.1.2 Sample Size and Power Analysis: Li et al. conducted an experiment similar to ours, measuring craving responses to DLPFC rTMS (Cohen's d = 3.0) or sham TMS (Cohen's d = 1.9).

Based on these estimates, we will need to recruit 15 subjects to each arm (total n=30) to detect similar differences with 80% power and 0.05 significance level. Our study should achieve similar power, even with up to 25% loss to follow-up in each arm. If our loss-to-follow up is only 10% per arm, we can detect an effect size as small as 0.962 with 80% power and 0.05 significance level. Our sample size is larger or similar to other studies using similar methods.

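### Section G commits in advance to reading a null result as evidence that the insula matters less than reported; the design supports only a narrower statement

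*Combined protocol and SAP*

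**What the plan says.** Section G sets out how a result with no difference in craving or fMRI will be read: "our interpretation will be that the insula is not as critical a neural node as the literature to date reports". It says such a result would turn the team's future work toward prefrontal targets, and closes with "Regardless of outcome, this proposal will answer a critically important question", namely how important the insula is in craving. Section G attaches no condition about precision, confidence intervals or whether the insula was in fact modulated.

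The size of the craving comparison is set in F.1.2 from a study "measuring craving responses to DLPFC rTMS (Cohen's d = 3.0) or sham TMS (Cohen's d = 1.9"). With 10% loss per arm, the plan says "we can detect an effect size as small as 0.962 with 80% power and 0.05 significance level". The analysis model in F.1.1 is different in form: "we will fit a general linear multivariate model, with measures of craving before and after treatment as the outcomes", with treatment assignment and FTND as predictors. For imaging, F.2.2 and F.3.2 give "Our sample size n=32 (after 10% attrition of fMRI data, 10% attrition of TMS administration"), and F.2.1 sets a voxel-wise threshold of p<0.005 with family-wise p<0.05, which F.3.1 carries over to Aim 3.

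Section C.3 also plans spectroscopy before and after stimulation: "1H-MRS examinations will be performed to quantify GABA, Glutamate, and Glutamine levels in the insula". C.10 labels its analysis exploratory. Section E acknowledges that the stimulation may also reach the lateral inferior frontal gyrus, which lies over the target.

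**The concern.** A non-significant result supports a negative conclusion only as far as its confidence interval excludes effects that matter, and only if the intervention did what it was meant to do. Section G requires neither. Two gaps follow.

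- **Precision.** The trial is sized for a very large craving effect, so a null may simply be a moderate effect that was missed.
- **Engagement.** Aims 2 and 3 are the evidence that stimulation changed the insula. Section G describes the case in which they are null as well. One session may then have failed to modulate the insula, which says nothing about how much the insula matters.

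At stake is what the trial may conclude. Followed as written, Section G would turn a result that is inconclusive for moderate effects into a negative statement about the insula and a reason to move to other targets.

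**Working it through.** **Inputs.** 20 per arm (Section I). Craving effects of 3.0 and 1.9, 15 per arm required, 10% and 25% loss, and 0.962 (F.1.2). Imaging n = 32, taken here as 16 per arm (F.2.2, F.3.2). Voxel-wise p<0.005 (F.2.1). F.1.2 names no test; a two-sided two-sample t-test is inferred because it reproduces the plan.

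**Formulas.** With n per arm and standardised difference d, df = 2n − 2 and noncentrality = d × √(n/2). Power is the probability that the noncentral t exceeds the two-sided critical value in absolute size. The half-width of the 95% CI, in SD units, is t(0.975, df) × √(2/n).

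**Reproducing the plan.**
- d = 3.0 − 1.9 = 1.1. At 14 per arm power is 79.99%, just short; at 15 per arm it is 82.8%. Plan: 15.
- 20 × 0.90 = 18 per arm. The effect detectable with 80% power is 0.961. Plan: 0.962.
- 20 × 0.75 = 15 per arm, consistent with the plan's 25% loss.

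**Craving, 18 per arm, alpha 0.05.**

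| d | noncentrality (d × 3) | power |
|---|---|---|
| 0.5 | 1.5 | 30.8% |
| 0.8 | 2.4 | 64.5% |
| 1.1 | 3.3 | 89.4% |

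Half-width: t(0.975, 34) × √(2/18) = 2.032 × 0.333 = 0.68 SD. An observed difference of exactly zero still leaves 0.68 SD inside the interval. A result just short of significance leaves about 2 × 0.677 = 1.35 SD inside it.

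**Sensitivity to the inferred test.** The plan states no correlations, so these are assumptions.
- If covariates correlate 0.3, 0.5 or 0.7 with the outcome, power at d = 0.5 is 33%, 39% or 53%.
- If craving is analysed as a change score and the effect is in single-occasion SD, the SD factor is √(2(1 − r)). For pre-post r of 0.3, 0.5 or 0.7, power is 23%, 31% or 47% at 0.5 SD, and 77%, 89% or 98% at 1.1 SD.

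**Imaging, 16 per arm.**

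| d | one test at 0.05 | one voxel at 0.005 (illustrative) |
|---|---|---|
| 0.5 | 28% | 7% |
| 0.8 | 59% | 25% |
| 1.1 | 85% | 54% |

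Neither column is the power of the planned cluster-corrected test, which needs information that the documents do not give.

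**Engagement.** C.6 and F.3.1 measure connectivity from, and activity in, a 5 mm sphere at the stimulation target. If both are null, two explanations fit the same data: the insula was not modulated, or it was modulated and does not matter. Spectroscopy could help separate them, since "Exploratory analysis of the changes in GABA, glutamate, and glutamine concentrations induced by rTMS will be performed", but it has no stated power and Section G does not use it.

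**The case against.** The strongest reply has three parts.

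**Section G is narrative, and its claim is relative.** It is not the analysis plan, and it says less critical than reported, not unimportant. The lesion literature cited in Section II describes very strong effects. This stands in part and is why the point is minor. But the statement is still about the insula rather than about this procedure. The benchmark does not help either: the 1.1 SD in F.1.2 comes from DLPFC stimulation, and the imaging effects in F.2.2 and F.3.2 come from prefrontal targets. Missing them does not measure the insula against its own literature.

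**A null on everything is stronger evidence than a null on craving.** This is true as far as it goes. For illustration, assume the same d on three independent outcomes, each tested at 0.05. The chance of a full null is 0.106 × 0.147² = 0.2% at d = 1.1, 0.355 × 0.409² = 6% at 0.8, and 0.692 × 0.722² = 36% at 0.5. With one voxel at 0.005 for each imaging outcome, the same products are 0.106 × 0.46² = 2%, 0.355 × 0.755² = 20% and 0.692 × 0.931² = 60%. Positive correlation between outcomes raises these chances. Moderate effects stay open, and the engagement problem does not depend on power.

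**The plan already recognises limits.** Section E admits stimulation of overlying cortex, proposes exploratory checks of all structures in the field, and notes that connectivity may change without activity. That is fair, but none of it is carried into the reading of a null in Section G.

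A reader might infer that a null would be uninformative, or that the sample size is wrong. The documents do not support either. The plan's craving figures reproduce, and a craving null does count against effects near 1.1 SD.

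**Conclusion.** The point holds as a minor one about interpretation. For craving, a null makes effects near 1.1 SD from the stimulation as delivered unlikely (power 89% at 18 per arm) and leaves moderate effects open (31% at 0.5 SD, 64% at 0.8 SD; half-width about 0.68 SD). For fMRI no bound of this kind can be stated. A reader might extend the 1.1 SD bound to imaging; the planned voxel-wise threshold and cluster correction do not allow that. If Aims 2 and 3 are null too, the data cannot separate failure to modulate the insula from an unimportant insula.

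A reader might also infer that the trial's analyses or conduct are compromised. They are not: no test, estimate or participant procedure depends on Section G.

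The figures rest on the inferred t-test, 18 and 16 per arm with balanced losses, and a common SD behind the difference 3.0 − 1.9. The planned multivariate model may be more or less precise. In the ranges tried, power at 0.5 SD ran from 23% to 53%.

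**What to change.** Replace the sentence on a null result in Section G with text such as:

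> If no between-arm difference is observed, we will report the between-arm difference in QSU-brief change and in target-ROI activity with 95% confidence intervals, and state which effect sizes they exclude. The conclusion will be limited to this single-session stimulation as delivered. If Aims 2 and 3 are also null, failure to engage the insula cannot be excluded, and no conclusion about the importance of the insula will be drawn. Insular MRS change will be reported as exploratory supporting evidence.

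Qualify the closing claim that the question is answered whatever the outcome in the same way. QSU-brief change is proposed because A.1 names it as the primary cognitive outcome; the target ROI is already extracted under F.3.1.

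A relevance bound for craving, fixed before unblinding, is optional. With a true difference of zero and 18 per arm, the interval would exclude a benefit of 0.5, 0.8 or 1.1 SD in about 31%, 64% or 89% of trials. With a bound near 0.5 SD, most nulls would therefore be inconclusive.

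**Cost.** Wording in Section G, plus two between-arm differences with confidence intervals, a small addition to the planned multivariate and voxel-wise tests. The downside is that a null would support a weaker statement than the plan now promises.
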